7.2 Serious adverse event (SAE)

7.2.1 Definition of a SAE

A SAE is defined as any adverse event (appearance of (or worsening of any pre-existing) undesirable sign(s), symptom(s) or medical conditions(s) which meets any one of the following criteria:

- is fatal or life-threatening
- results in persistent or significant disability/incapacity
- constitutes a congenital anomaly/birth defect
- requires inpatient hospitalization or prolongation of existing hospitalization, unless hospitalization is for:
 - routine treatment or monitoring of the studied indication, not associated with any deterioration in condition (specify what this includes)
 - elective or pre-planned treatment for a pre-existing condition that is unrelated to the indication under study and has not worsened since signing the informed consent
 - treatment on an emergency outpatient basis for an event not fulfilling any of the definitions of a SAE given above and not resulting in hospital admission
- social reasons and respite care in the absence of any deterioration in the patient's
- general condition
- is medically significant, i.e. defined as an event that jeopardizes the patient or may require medical or surgical intervention.

Life-threatening in the context of a SAE refers to a reaction in which the patient was at risk of death at the time of the reaction; it does not refer to a reaction that hypothetically might have caused death if more severe (see ICH-E2D Guideline available at:

http://www.ich.org/fileadmin/Public_Web_Site/ICH_Products/Guidelines/Efficacy/E2D/Step4/E2D_Guideline.pdf).

All malignant neoplasms will be assessed as serious under “medically significant” if other seriousness criteria are not met.

Any suspected transmission via a medicinal product of an infectious agent is also considered a serious adverse reaction.

Medical and scientific judgment should be exercised in deciding whether other situations should be considered serious reactions, such as important medical events that might not be immediately life threatening or result in death or hospitalization but might jeopardize the patient or might require intervention to prevent one of the other outcomes listed above. Examples of such events are intensive treatment in an emergency room or at home for allergic bronchospasm, blood dyscrasias or convulsions that do not result in hospitalization or development of dependency or abuse (see ICH-E2D Guideline available at:

http://www.ich.org/fileadmin/Public_Web_Site/ICH_Products/Guidelines/Efficacy/E2D/Step4/E2D_Guideline.pdf).

7.2.2 Serious adverse event reporting

To ensure patient safety, every SAE, regardless of causality, occurring after the patient has provided informed consent and until 30 days [after the last study visit/ following the last administration of study treatment if there are post-treatment follow-up visits with no required procedures] must be reported to Novartis within 24 hours of learning of its occurrence. Any SAEs experienced after the 30 days period should only be reported to Novartis if the investigator suspects a causal relationship to study treatment.

Recurrent episodes, complications, or progression of the initial SAE must be reported as follow-up to the original episode, regardless of when the event occurs. This report must be submitted within 24 hours of the investigator receiving the follow-up information. An SAE that is considered completely unrelated to a previously reported one should be reported separately as a new event.

Information about all SAEs (*either initial or follow up information*) is collected and recorded on the paper Serious Adverse Event Report Form. The investigator must assess the relationship to *the study treatment* complete the SAE Report Form in English, and send the completed, signed form by fax within 24 hours after awareness of the SAE to the local Novartis Drug Safety and Epidemiology Department. The telephone and fax number of the contact persons in the local department of Drug Safety and Epidemiology, specific to the site, are listed in the investigator folder provided to each site. The original copy of the SAE Report Form and the fax confirmation sheet must be kept with the case report form documentation at the study site. Follow-up information should be provided using a new paper SAE Report Form stating that this is a follow-up to a previously reported SAE

Follow-up information provided should describe whether the event has resolved or continues, if and how it was treated whether the patient continued or withdrew from study participation. Each re-occurrence, complication, or progression of the original event should be reported as a follow-up to that event regardless of when it occurs.

If the SAE is not previously documented in the SmPC (see appendix 1) (new occurrence) and is thought to be related to the study treatment a Drug Safety and Epidemiology Department associate may urgently require further information from the investigator for Health Authority reporting. Novartis may need to issue an Investigator Notification (IN) to inform all investigators involved in

any study with the same investigational treatment that this SAE has been reported. Suspected Unexpected Serious Adverse Reactions (SUSARs) will be collected and reported to the competent authorities and relevant ethics committees in accordance with Directive 2001/20/EC or as per national regulatory requirements.

7.3 Pregnancy reporting

To ensure patient safety, each pregnancy occurring while the patient is on study treatment must be reported to Novartis within 24 hours of learning of its occurrence. The pregnancy should be followed up to determine outcome, including spontaneous or voluntary termination, details of the birth, and the presence or absence of any birth defects, congenital abnormalities, or maternal and/or newborn complications.

Pregnancy should be recorded on a Clinical Trial Pregnancy Form and reported by the investigator to the local Novartis Drug Safety and Epidemiology Department. Pregnancy follow-up should be recorded on the same form and should include an assessment of the possible relationship to the study treatment.

Any SAE experienced during pregnancy must be reported on the SAE Report Form.

8 Data review and database management

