Study drug/ treatment	Any single drug or combination of drugs administered to the patient as part of the required study procedures; includes investigational drug (s), active drug run-ins or background therapy
Study/investigational treatment discontinuation	Point/time when patient permanently stops taking study/investigational treatment for any reason; may or may not also be the point/time of premature patient withdrawal
Variable	Information used in the data analysis; derived directly or indirectly from data collected using specified assessments at specified time points

Amendment 5

Changes to the protocol are related to the following sections:

- Section 4.1. inclusion criteria

The current version of inclusion criteria stipulates that *"patients who have completed the international CACZ885G2306 study and who successfully withdrew canakinumab treatment per protocol but with a disease relapse within one year from the End of study visit will be allowed to participate in CACZ885GFR01 study"*.

The purpose of the change is to enable these patients who experienced a relapse to be included in the local extension study CACZ885GFR01 with no time limitation after the end of study visit.

Canakinumab is still not commercially available in France in the SJIA (Systemic Juvenile Idiopathic Arthritis) indication at the date of the amendment 5. The inclusion in the local extension study is the only option to treat these patients and to resume canakinumab, when medically justified.

- Section 5. Treatment

For patients previously included in study CACZ885G2301E1 (SJIA), the option to interrupt canakinumab after a prolonged remission according to the investigators judgment has been added.

Every patient withdrawn from CACZ885GFR01 study due to a remission will be allowed to resume canakinumab in case of relapse and will be followed up again in the study.

- Section 5.1.1 . Investigational treatment

Novartis has been supplying the open-label investigational drug (canakinumab) under the form of a lyophilisate in vial. A marketing authorization has been granted in February 2017 by the European

Commission for canakinumab as a solution for injection.

If necessary (for logistic reasons), Novartis may supply one or the other pharmaceutical form for the trial. There will not be any change for the patient in the way the medication is administered (subcutaneously).

Amendment 4

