1.1 Background

Systemic Juvenile Idiopathic Arthritis (SJIA) is a subset of Juvenile Idiopathic Arthritis (JIA), a serious and potentially disabling form of arthritis that occurs in children 16 years of age and younger, and accounts for approximately 4 - 17 % of JIA (Quartier 2007, Ravelli and Martini 2007). In contrast to other JIA subtypes SJIA is associated with systemic symptoms such as fever, rash, anemia, leukocytosis, elevated erythrocyte sedimentation rate and acute-phase. The peak age of disease onset lies between 18 months and 2 years, but SJIA may occur in children of any age and, rarely, in young adults too (Woo 2006).

Several lines of evidence show that interleukin-1 (IL-1) plays a pivotal role in the pathogenesis of SJIA (Dinarello 2005, Pascual et al 2005).

Ilaris[®] (Canakinumab) is a human monoclonal anti-human interleukin-1 beta (IL-1 beta) antibody of the IgG1/ κ isotype. Canakinumab binds with high affinity specifically to human IL-1 beta and neutralizes the biological activity of human IL-1 beta by blocking its interaction with IL-1 receptors, thereby preventing IL-1 beta-induced gene activation and the production of inflammatory mediators. Canakinumab has a half-life of approximately 21-28 days.

To date, four clinical studies (CACZ885A2203, CACZ885G2305, CACZ885G2301, and CACZ885G2301E1) have been performed by Novartis to evaluate canakinumab as a treatment for patients with SJIA.

Ilaris[®] received Marketing Authorization by the EMA for patients with Systemic Juvenile Idiopathic Arthritis (SJIA) on August 2013 for *the treatment of active Systemic Juvenile Idiopathic Arthritis (SJIA) in patients aged 2 years and older who have responded inadequately to previous therapy with non-steroidal anti-inflammatory drugs (NSAIDs) and systemic corticosteroids. Ilaris[®] can be given as monotherapy or in combination with methotrexate.*

Study CACZ885G2301E1 is a Phase III study designed to assess long-term safety and efficacy data for patients with SJIA who either participated in the CACZ885G2305 and CACZ885G2301 registration studies or were treatment-naïve to canakinumab. In France, 48 patients were enrolled in the CACZ885G2301E1 study at four centers (Necker, Kremlin- Bicêtre, Lyon, and Strasbourg). Study CACZ885G2301E1 is ending on November 2014 and 3 sites (Necker, Kremlin-Bicêtre, and Lyon) still have patients under treatment.

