4.2 Exclusion criteria

1. History of recurring infections, or underlying conditions which may predispose them to infections. Treatment with canakinumab should not be continued in patients with severe infections requiring medical intervention.
2. Hypersensitivity to the active substance or to any of the excipients (see SmPC, section 6.1).
3. Concomitant use of second line agents such as disease-modifying and/or immunosuppressive drugs will not be allowed with the exception of:
 - Methotrexate, and folic/folinic acid supplementation (according to standard medical practice)
 - Non-steroidal anti-inflammatory drug (NSAID)
 - Systemic corticosteroid treatment.
4. Concomitant use of another biologic agent or any investigational drug.
5. Pregnant or nursing (lactating) female patients, where pregnancy is defined as the state of a female after conception and until the termination of gestation, confirmed by a positive hCG laboratory test or an urinary pregnancy test.
6. Female patients who are of child-bearing potential, defined as all females physiologically capable of becoming pregnant, unless they are using effective methods of contraception during dosing of study treatment. Effective contraception methods include:
 - Total abstinence (when this is in line with the preferred and usual lifestyle of the subject). Periodic abstinence (e.g., calendar, ovulation, symptothermal, post- ovulation methods) and withdrawal are not acceptable methods of contraception

- Female sterilization (have had surgical bilateral oophorectomy with or without hysterectomy) or tubal ligation at least six weeks before taking study treatment. In case of oophorectomy alone, only when the reproductive status of the woman has been confirmed by follow up hormone level assessment
- Male sterilization (at least 6 months prior to inclusion). For female subjects on the study, the vasectomized male partner should be the sole partner for that subject
- Barrier methods of contraception: Condom or Occlusive cap (diaphragm or cervical/vault caps) with spermicidal foam/gel/film/cream/vaginal suppository
- Use of oral, injected or implanted hormonal methods of contraception or other forms of hormonal contraception that have comparable efficacy (failure rate
- <1%), for example hormone vaginal ring or transdermal hormone contraception
- Placement of an intrauterine device (IUD) or intrauterine system (IUS)

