In case of use of oral contraception women should have been stable on the same pill for a minimum of 3 months before taking study treatment.

Reliable contraception should be maintained throughout the study and until 3 months after canakinumab discontinuation.

5 Treatment

Initial canakinumab dose:

For patients previously included in study CACZ885G2301E1 (SJIA)

Patients will continue the same dose as their last dose administered in the study CACZ885G2301E1: canakinumab 4mg/kg (or 300mg max) or 2mg/kg (150mg max) every 4 weeks.

Canakinumab dose reduction from 4 mg/kg to 2 mg/kg every 4 weeks in steroid-free patients with prolonged strong response was permitted in the ongoing extension study CACZ885G2301E1 at the request of the treating physician and with the agreement of Novartis.

Similarly, in this study, the canakinumab dose may be reduced from 4mg/kg (300 mg max) to 2mg/kg (150 mg max) every 4 weeks and then interrupted after a prolonged remission according to the investigators judgment.

For patients previously included in study CACZ885N2301 (Periodic Fever syndromes indications: TRAPS, HIDS or crFMF)

Patients will continue one of the following regimens as received at the end of the study:

- canakinumab 150 mg (or 2 mg/kg for patients weighing ≤ 40 kg) q4w
- canakinumab 150 mg (or 2 mg/kg for patients weighing ≤ 40 kg) q8w
- canakinumab 300 mg (or 4 mg/kg for patients weighing ≤ 40 kg) q4w
- canakinumab 300 mg (or 4 mg/kg for patients weighing ≤ 40 kg) q8w

In case of re-flare (according to investigators judgment), patients will be allowed to increase the dose as follow:

- If patients receive canakinumab 150 mg q8w, the dose of canakinumab will be increased to 150 mg q4w
- If patients receive canakinumab 150 mg q4w, the dose of canakinumab will be increased to 300 mg q4w
- If patients receive canakinumab 300 mg q8w, the dose of canakinumab will be increased to 300 mg q4w

For patients previously included in study CACZ885G2306 (SJIA):

The patients will continue the same dose as their last dose administered at the end of the tapering period study CACZ885G2306.

Then, patients will continue one of the following regimens:

- Canakinumab 4mg/kg q4wks
- Canakinumab 2mg/kg q4wks
- Canakinumab 1mg/kg q4wks
- Canakinumab 4mg/kg q8wks
- Canakinumab 4mg/kg q12wks

The patients who have withdrawn canakinumab per protocol may resume canakinumab after a relapse at a starting dose of 4 mg/kg (maximum 300 mg) every 4 weeks.

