10.2 Informed consent procedures

Eligible patients may only be included in the study after providing written (witnessed, where required by law or regulation), IRB/IEC-approved informed consent, or, if incapable of doing so, after such consent has been provided by a legally acceptable representative of the patient. In cases where the patient's representative gives consent, the patient should be informed about the study to the extent possible given his/her understanding. If the patient is capable of doing so, he/she should indicate assent by personally signing and dating the written informed consent document or a separate assent form. Informed consent must be obtained before conducting any study-specific procedures (i.e. all of the procedures described in the protocol). The process of obtaining informed consent should be documented in the patient source documents.

Novartis will provide to investigators in a separate document a proposed informed consent form that complies with the ICH GCP guideline and regulatory requirements and is considered appropriate for this study. Any changes to the proposed consent form suggested by the investigator must be agreed to by Novartis before submission to the IRB/IEC, and a copy of the approved version must be provided to the Novartis monitor after IRB/IEC approval.

Women of child bearing potential should be informed that taking the study treatment may involve unknown risks to the fetus if pregnancy were to occur during the study and agree that in order to participate in the study they must adhere to the contraception requirement for the duration of the study. If there is any question that the patient will not reliably comply, they should not be entered in the study.

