2.1.1 General definitions

Study treatment: refers to: Ilaris = ACZ885

Study treatment start and end date: Study treatment start date is defined as the first date of study drug is administered and recorded on the Study Medication Dosing Record in CRF page. Similarly, study drug end date is defined as the last date of study drug is administered.

Study day: Study day will be calculated as (event date – study drug start date + 1 day) for events that occurred on or after study drug start date (e.g. visit, adverse events). For events prior to study drug start date (e.g., time of diagnosis), study day will be negative and calculated as (event date – study drug start date).

Baseline and post baseline: In general, a *baseline* value refers to the last measurement made prior to administration of the first dose of study treatment or the average values taken prior to administration of the first dose of study treatment. A post-baseline value refers to a measurement taken after the first dose of study treatment.

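### Section 7.3 sets no pregnancy-reporting window after treatment, although section 4.2 asks for contraception until 3 months after canakinumab is stopped

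*Protocol*

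**What the plan says.** **Pregnancy.** Protocol section 7.3 requires that "each pregnancy occurring while the patient is on study treatment must be reported to Novartis within 24 hours of learning of its occurrence". Such a pregnancy is followed to its outcome, and any SAE during it goes on the SAE form. No days after treatment are stated, and being on study treatment is not defined. The nearest definitions are the glossary entry for treatment discontinuation ("Point/time when patient permanently stops taking study/investigational treatment for any reason") and SAP section 2.1.1, where "study drug end date is defined as the last date of study drug is administered".

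**Contraception.** The duration is worded in three ways:
- Exclusion criterion 6 (section 4.2, and the synopsis) excludes women of child-bearing potential "unless they are using effective methods of contraception during dosing of study treatment".
- The sentence that closes section 4.2 reads "Reliable contraception should be maintained throughout the study and until 3 months after canakinumab discontinuation".
- Section 10.2 asks women to agree that "they must adhere to the contraception requirement for the duration of the study".

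**Related rules.** Section 1.1 states "Canakinumab has a half-life of approximately 21-28 days". Section 7.2.2 requires all SAEs to be reported for 30 days whatever their cause, and later ones only if the investigator suspects the drug. Section 7.2.1 counts a congenital anomaly as an SAE. Section 5 lets the last dose be given at the last visit. The visit table in section 6 shows no visit after the end-of-study visit and no pregnancy test.

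**The concern.** By asking for contraception for 3 months after discontinuation, the protocol treats those months as a time when pregnancy should be avoided. It then creates no duty to report a pregnancy that occurs in them. Collecting safety data is the study's only data objective (section 2), and the drug clears slowly, so an early post-dose pregnancy is an exposed one.

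What is at stake is selective capture. A pregnancy that ends badly may come in through the SAE route. One that ends normally has no required route. Anyone reading the safety data later would see some adverse outcomes without the number of exposed pregnancies they came from.

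**Working it through.** There is no stated figure to reproduce: the plan has no sample size calculation, test or pregnancy analysis. The check compares the windows and then applies simple decay.

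**Inputs**
- Pregnancy reporting: while on study treatment, no days added (section 7.3).
- Contraception: until 3 months after discontinuation (end of section 4.2). I take 3 months as 90-92 days; this is an assumption.
- SAE reporting whatever the cause: 30 days (section 7.2.2). The start of the clock is given as bracketed alternatives, the last study visit or the last administration. I assume the two coincide, as section 5 allows.
- Half-life: 21-28 days (section 1.1).

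**Step 1: windows after the last dose**
- Strict reading, with treatment ending at the last administration: 0 days of pregnancy reporting against 90-92 days of contraception.
- Looser reading, with a patient counted as on treatment until her next dose would have been due: 4 × 7 = 28 days on a 4-week interval, up to 12 × 7 = 84 days on a 12-week interval. Both fall short of 90 days, and the text supports neither reading explicitly.
- SAE window: 30/90 = 33% of the period. That leaves 90 − 30 = 60 to 92 − 30 = 62 days in which only SAEs suspected to be related must be reported.

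**Step 2: drug remaining**

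Fraction remaining = 2^(−t / half-life), assuming first-order elimination.

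| Days after last dose | Half-life 21 d | Half-life 28 d |
|---|---|---|
| 30 | 2^(−1.43) = 37.1% | 2^(−1.07) = 47.6% |
| 90 | 2^(−4.29) = 5.1% | 2^(−3.21) = 10.8% |
| 92 | 2^(−4.38) = 4.8% | 2^(−3.29) = 10.3% |

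**Step 3: what must be reported, by case**

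| Pregnancy | Must it be reported as a pregnancy? | Other routes |
|---|---|---|
| Begins on treatment, learned of at any time | Yes, and followed to outcome | SAE form |
| Begins after the last dose, uncomplicated | No | Voluntary only |
| Begins after the last dose, with an SAE | No | SAE within 30 days, or later if suspected related |
| Begins during an interruption or after withdrawal for remission | Not settled for an interruption; no on the plain wording for a withdrawn patient | As above; week 13 visit if still in the study |

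The second row is the gap. Part of the fourth adds to it, because section 5 allows treatment to be interrupted after prolonged remission and lets withdrawn patients come back after relapse.

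**The case against.** The strongest reply is that the protocol has several other safety routes.
- A pregnancy begun on treatment is followed to birth, defects included, independently of the 30-day SAE window.
- Suspected-related SAEs are reportable with no end date, and a congenital anomaly is an SAE.
- Section 7.1 has patients told to report later events that they or their physician think may be related.
- A patient with no dose for 12 weeks who remains in the study has a safety visit at week 13.

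All of this stands. A reader might infer that exposed pregnancies after the last dose would never be captured, and these routes rule that out. They do not close the gap, because each depends on a serious event, a suspicion of causality or a chance mention. None brings in an uncomplicated pregnancy as a matter of duty.

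Three further points also stand.
- A reader might infer that women are told the shorter contraception period at consent. Section 10.2 is protocol text; the consent form is a separate document that is not available here, and section 10.2 may simply point to the requirement in section 4.2.
- Within section 4.2, the reference to dosing can be read as the entry condition and the closing sentence as its extension. The clearest mismatch is then with section 10.2 and the synopsis.
- A temporarily interrupted patient can be read as still on treatment, since the glossary ties discontinuation to a permanent stop. The wording is unclear on interruptions; it does not plainly exclude them.

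**Conclusion.** The gap is real and narrow. A pregnancy conceived after the last dose but before the protocol's own contraception period ends need not be reported as a pregnancy, at a time when about 37-48% (day 30) falling to 5-11% (day 90) of the drug remains. These percentages describe exposure. They do not count missed pregnancies.

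The number of women affected cannot be derived. It is bounded by total enrolment of up to 40 (synopsis) or 41 (section 4), drawn largely from paediatric studies. It would be wrong to assume a 90-day washout for every woman, because the planned end of study is availability of reimbursed drug and patients who move directly to it are not in washout.

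A reader might also infer a biased estimate. Neither protocol section 9 nor the SAP plans a pregnancy summary, and there is no hypothesis test, so no planned result changes. The loss is in completeness of safety data.

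The conclusion rests on treatment ending at the last administration, on 3 months being 90-92 days, and on first-order elimination. The looser reading of treatment shortens the gap but does not remove it. The change is worth making because it is cheap and serves the study's stated objective.

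**What to change.** Amend section 7.3 so that every pregnancy the site learns of, beginning at any time from the first dose to the end of the contraception period the protocol sets, is reported within the existing 24 hours and followed to outcome. State that treatment interruptions and withdrawals for remission are included, and define when a patient counts as on study treatment. Say how the duty applies to patients who move to commercial drug.

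Reconcile the contraception wording in the synopsis, exclusion criterion 6, the closing sentence of section 4.2 and section 10.2 so that one duration applies, and check the consent form against it. Which duration is right is for the sponsor; the reporting window should follow whatever is confirmed.

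The cost is a slightly longer passive reporting duty for sites, aligned wording and few extra reports. No visit needs to be added. The limit is that passive reporting depends on the patient telling the site. Active capture would need a contact after the end-of-study visit, which would cost more and is not proposed here.
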